6 STUDY CONDUCT

6.1 General Instructions

This is a pilot, randomized, open-label, active comparator, US, single-center trial in which patients will be randomized to receive HyBryte or Valchlor in a 1:1 randomization. Patients will be treated for 12 weeks and follow-up visits will be conducted 1, 2, and 4 weeks after completion of the treatment phase of the trial.

Patients randomized to HyBryte will have HyBryte applied twice weekly and an opaque covering applied for 21 (± 3) hours followed by the administration of visible light encompassing wavelengths of 500 to 650 nm. The light will be administered with a precisely calibrated device with a light dose starting at 6 J/cm² twice weekly that is titrated up according to the physician's discretion on subsequent sessions, limited by occurrence of Grade 2 erythema or greater but targeting a mild, Grade 1 reaction immediately following the light treatment. All of the patient's lesions that are readily available for exposure to the visible light source will be treated.

Patients randomized to Valchlor will apply a thin film of Valchlor gel once daily to affected areas of the skin and the dosing will follow the instructions for use in the package insert.

Prior to randomization, each patient will have at least 3 and up to 5 index lesions identified. These lesions should be representative of the patient's treated lesions and, if the patient has both plaque and patch lesions, include approximately the same distribution as the patient's other lesions.

6.2 Study Procedures by Time Point

6.2.1 Screening

Patients will be screened up to 30 days prior to randomization. At the screening visit the following will be done:

- Signed, Informed Consent Form obtained
- Inclusion/exclusion criteria reviewed
- Complete medical history completed
- Women of child-bearing potential will have a serum pregnancy test obtained

6.2.2 Baseline

At the Baseline visit, the following will be done prior to randomization:

- Confirmation that the patient meets all inclusion/exclusion criteria
- History of any medical changes obtained
- Women of child-bearing potential will have a serum pregnancy test obtained unless the screening test was obtained 7 days or less
- Physical exam
- Vital signs obtained
- Blood for the hematology panel obtained
- Blood for the clinical chemistry panel obtained
- Three to five lesions that are representative of the patient's disease and are discrete with defined borders, will be chosen as the index lesions, and classified as patch or plaque lesions
- Charting of all CTCL lesions on the "Body Lesion Diagram" ([APPENDIX III – Body Lesion Diagram](#)) locating and numbering each of the index lesions
- Each index lesion will have an mCAILS score assessed and recorded
- The mSWAT score will be assessed and recorded
- The SAEQ score will be collected and recorded
- The SCORD score will be collected and recorded

Once all of these assessments are completed, the patient will be randomized into one of the two treatment arms, to receive HyBryte or Valchlor as the study drug. Patients who are randomized into the HyBryte treatment arm will follow the assessments outlined in Section [6.2.3](#). Patients who are randomized into the Valchlor treatment arm will follow the assessments outlined in Section [6.2.4](#).

6.2.3 *HyBryte Patients*

Patients who are randomized into the HyBryte treatment arm will be given a jar of ointment at the Baseline visit. They will be instructed on proper drug application and demonstrate proficiency in drug application and all accessible lesions will be treated with study drug.

6.2.3.1 *Standard light treatment clinic visits*

Patients randomized to HyBryte will have HyBryte applied twice weekly and an opaque covering applied for 21 (± 3) hours followed by the administration of visible light encompassing wavelengths of 500 to 650 nm. The light will be administered with a precisely calibrated device with a light dose starting at 6 J/cm² twice weekly that is titrated up according to the physician's discretion on subsequent sessions. Treatment will target a post-light treatment Erythema score of 1. The light dose will be reduced, maintained or treatment administrations may be suspended if a Grade 2 or greater erythema is present. Additional assessments of treated lesions and surrounding areas will include:

- Erythema
- Pain
- Pruritus
- Edema
- Hyperpigmentation
- Hypopigmentation
- Rash
- Vesiculation

Each dermatological assessment will be graded according to [Table 4](#). All of the patient's lesions that are readily available for exposure to the visible light source will be treated.

Table 4: Dermatologic Assessment Grading

Toxicity Grade:	Severity
Grade 0	No apparent reaction
Grade I	Mild
Grade II	Moderate
Grade III	Severe
Grade IV	Life-threatening

At each visit, the following assessments will be conducted:

- Interval medical history obtained

- Any AEs documented
- Adequate application of the drug will be verified by a pink staining on visual inspection of lesions prior to administration of light
- Delivery of light session, the time of treatment calculated by the target dose (starting at 6 J/cm² and titrated up at the Investigator's discretion to a dose that generates an Erythema score >1 at the treated lesions or 25 J/cm², whichever occurs first)
- A dermatologic assessment of treated lesions will be performed immediately before and 10 to 30 minutes following completion of the light session.

6.2.3.2 *Week 3 Session 6, Week 6 Session 12, and Week 9 Session 18*

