
Methodology: This will be an open-label trial enrolling patients with CTCL (stage IA, IB, or IIA) randomized to receive topical HyBryte or topical Valchlor for 12 weeks.
 
Patients randomized to HyBryte will apply the drug to all accessible lesions twice per week followed by visible light treatment 21 (± 3) hours later starting at 6 J/cm² and titrated up at each visit until there is evidence of mild erythema of the treated lesions following the light session (Grade 1 erythema on the Erythema Score) and dropping the light dose if there is Grade 2 erythema. Should the patient have Grade ≥ 3, treatment will be suspended for 1 week and treatment may be restarted at a 1 J/cm² lower than the last well-tolerated light dose.
 
Patients randomized to Valchlor will receive commercially available drug applied as per the package insert.
 
Three to 5 prospectively identified index lesions will be evaluated for mCAILS assessment and the lesions chosen will be representative of the patient's overall disease and, if the patient has both patch and plaque lesions, the index lesions should include each type in the approximate same percentage as their total lesions.
 
Patients will be treated for a total of 12 weeks, with follow-up visits at Week 13, Week 14, and Week 16/End of Study. Every three weeks, patients will come to the clinic for an assessment visit (ie, at Week 3, Week 6, Week 9, and Week 12). At these evaluation visits, a cumulative mCAILS, modified Severity-Weighted Assessment Tool (mSWAT), Physician Global Assessment (PGA), Skin Adverse Event Questionnaire (SAEQ) will be completed, and Scoring Dermatitis (SCORD) collected.
 
For HyBryte patients, these assessments will be done immediately prior to light treatment at the second light treatment visit of the evaluation week (ie, Weeks 3, 6, 9, 12).
 
Follow-up assessments will be conducted at Week 13 (1-week post-treatment), Week 14 (2 weeks post-treatment), and Week 16/End of Study (4 weeks post-treatment) and will also include mCAILS, mSWAT, PGA, SAEQ, and SCORD assessments.
 
Physical examinations and safety labs (hematology and chemistry) will be analyzed at Baseline, at the Week 12 assessment visit, and 4 weeks after completion of therapy (Week 16/End of Study). AE's will be recorded throughout the study. Vital signs will be collected at Baseline and Weeks 3, 6, 9, 12, 13, 14 and 16.
		

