13. Subjects receiving drugs known to cause photosensitization within 2 weeks of starting HyBryte therapy unless they have not had evidence of photosensitization after receiving a stable dose of the medication for a minimum of 4 weeks

Name of Sponsor/Company: Soligenix, Inc.		(For National Authority Use only)
Name of Finished Product HyBryte™		
Name of Active Ingredient Hypericin (0.25% ointment)		

Test product, dose and mode of administration: HyBryte (0.25% hypericin) will be applied in a thin film on all lesions avoiding treatment of healthy skin. The drug will be activated 21 ± 3 hours after application starting at 6 J/cm^2 of visible light metered by duration of exposure and titrated up at each visit until a mild erythema (Grade I Erythema Score) in the treated lesions is seen following the light session and dropping the light dose if there is Grade 2 erythema. Should the patient have Grade ≥ 3, treatment will be suspended for 1 week and treatment may be restarted at a 1 J/cm^2 lower than the last well-tolerated light dose.
 
Valchlor will be administered in accordance with the FDA-approved package insert.
		

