6.2.3.2.1 Light Treatment Day

The patient will return to the clinic 21 (± 3) hours after study drug is applied and the following assessments will be conducted prior to light treatment:

- Each index lesion will have an mCAILS score assessed and recorded
- The mSWAT score will be assessed and recorded
- The PGA score will be assessed and recorded
- The SAEQ score will be collected and recorded
- The SCORD score will be collected and recorded

Once the assessments are completed, the standard light treatment procedures will be conducted, as follows:

- Interval medical history obtained
- Any AEs documented
- Adequate application of the drug will be verified by a pink staining on visual inspection of lesions
- Delivery of light session, the time of treatment calculated by the target dose
- A dermatologic assessment of treated lesions will be performed immediately before and 10 to 30 minutes following completion of the light session. This includes assessment of treated lesions and surrounding areas for:
 - Erythema

- Pain
- Pruritus
- Edema
- Hyperpigmentation
- Hypopigmentation
- Rash
- Vesication

6.2.3.3 Week 12 Session 24

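### Section 6.2.3.1 sets a light-dose titration endpoint above the Grade 1 target and weakens the synopsis's rules for Grade 2 and Grade ≥3 erythema

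*Combined protocol and SAP*

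**What the plan says.** The synopsis gives the light-dose rule twice, under Methodology and under Test product. The dose starts at 6 J/cm² and is "titrated up at each visit until there is evidence of mild erythema of the treated lesions following the light session". Methodology then calls for "dropping the light dose if there is Grade 2 erythema. Should the patient have Grade ≥ 3, treatment will be suspended for 1 week". The Test product entry completes the rule: "treatment will be suspended for 1 week and treatment may be restarted at a 1 J/cm^2 lower than the last well-tolerated light dose".

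Section 6.1 leaves titration to the physician, "limited by occurrence of Grade 2 erythema or greater but targeting a mild, Grade 1 reaction immediately following the light treatment".

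Section 6.2.3.1 deals with the dose in two places. Its narrative says "Treatment will target a post-light treatment Erythema score of 1" and adds "The light dose will be reduced, maintained or treatment administrations may be suspended if a Grade 2 or greater erythema is present". Its list of procedures for each visit then has the dose titrated up at the investigator's "discretion to a dose that generates an Erythema score >1 at the treated lesions or 25 J/cm², whichever occurs first".

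Table 4 grades reactions in whole steps from 0 to IV, with II moderate, III severe and IV life-threatening.

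**The concern.** Staff who set the exposure time at each session will work from the visit procedures in 6.2.3.1. That section gives two endpoints for titration. Its response to a skin reaction is also looser than the synopsis's. Someone following it to the letter could go on raising the dose after the intended mild reaction has been reached, or give the same dose after a severe one.

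This is a dosing rule that protects patients, so it matters whatever the sample size and although the analysis is descriptive. It also affects what the pilot can report. A preliminary safety assessment is a stated objective, and skin reactions are hard to interpret if the rule that limits them can be applied in different ways.

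**Working it through.** The plan gives no figure to reproduce, so the check sets the texts side by side. It assumes that the erythema score used for titration is graded on Table 4, the only scale given for reactions to light. The 0-to-8 erythema scale in Table 5 belongs to mCAILS.

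| Place | Titration endpoint | At Grade 2 | At Grade ≥3 | Dose cap |
|---|---|---|---|---|
| Synopsis (Methodology; Test product) | Grade 1 | Lower the dose | Suspend 1 week; any restart 1 J/cm² below the last well-tolerated dose | Not stated |
| 6.1 | Target Grade 1, limit at Grade 2 or above | The limit only | The limit only | Not stated |
| 6.2.3.1 narrative | Target score of 1 | Lower, keep, or possibly suspend | Same sentence as Grade 2 | Not stated |
| 6.2.3.1 visit bullet | Score above 1 | Nothing further | Nothing further | 25 J/cm² |

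Other places where a rule might stand:

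- 6.2.3.2.1 (Weeks 3, 6 and 9) and 6.2.3.3.1 (Week 12) rely on the standard procedures: "Once the assessments are completed, the standard light treatment procedures will be conducted, as follows". They add no dose rule.
- 6.3 gives general grounds for withdrawing a patient.
- 7.2.1 covers grading only.
- 8.1.4 covers application of the ointment only.

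**Step 1: what a score above 1 means.** On whole grades, the first value above 1 is Grade II. Section 7.2.1 has an average score recorded, but an average of whole grades can exceed 1 only if at least one of them is II or higher. The bullet's endpoint is therefore one grade above the target stated in the other three places.

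**Step 2: a patient who reaches Grade 1.** Under the synopsis the dose stops rising. Under the bullet it may rise until the score exceeds 1 or the dose reaches 25 J/cm².

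**Step 3: a patient who reaches Grade 2.** The synopsis lowers the dose. The 6.2.3.1 narrative is satisfied by lowering it, keeping it or suspending treatment.

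**Step 4: a patient who reaches Grade 3 or 4.** The synopsis suspends treatment for one week. At two sessions a week that is 1 × 2 = 2 sessions, or 2/24 = 8.3% of the planned course if they are not made up, which the documents do not say. The 6.2.3.1 sentence covers every grade from 2 upward. Keeping the dose satisfies it, so it requires no session off and no reduction.

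**Step 5: which text governs.** The documents do not say. The only precedence rule, in 8.2, concerns the Valchlor package insert.

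**The case against.** The strongest defence is that the texts can be followed together. The synopsis is part of the protocol the investigator agrees to follow, so its Grade ≥3 rule is in force. A site that lowers the dose at Grade 2 and suspends at Grade ≥3 complies with everything. The bullet can also be read as a ceiling: with the 25 J/cm² cap it names two stopping points, and the first coincides with the Grade 2 limit in 6.1. Exposure is small, too: one center, about five HyBryte patients, light given in clinic, grading before and after each session, on-site training, and an investigator free to withdraw a patient.

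Much of this stands, and it rules out several stronger readings that a reader might infer:

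- *The protocol aims at moderate erythema.* It does not. The narrative of 6.2.3.1 itself states a target of 1.
- *The body has no dose reduction or suspension.* It has both, as options. What is missing is the obligation, the duration and the restart dose.
- *Only the Valchlor arm has a skin-toxicity stop.* The narrative of 6.2.3.1 allows suspension for HyBryte. The Valchlor stop is in 8.2.4, taken from the package insert, not in that arm's visit procedures.
- *The cap's absence from the synopsis is a conflict.* A limit given only in the detailed procedure contradicts nothing.
- *The excess risk can be quantified.* The documents give no Grade ≥3 rate and no relation between light dose and erythema. Table 1 reports erythema as an adverse event, not as the post-light score.

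The defence does not remove the conflict. The ceiling reading still allows increases beyond Grade 1. Compatibility helps only a reader who knows to take the stricter text each time, and 6.2.3.1 does not say so. Training on the protocol cannot settle what the protocol leaves inconsistent, and the right to withdraw a patient sets no light dose.

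**Conclusion.** The point holds as a conflict between stated dosing rules, and it should be corrected. Section 6.2.3.1 disagrees with the synopsis and with itself on the titration endpoint, by one grade. It turns the synopsis's Grade 2 reduction into an option and does not carry over the compulsory force, the one-week length or the restart dose of the Grade ≥3 suspension. For a patient with a severe reaction, that is a fixed one-week stop against no required action.

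The conclusion rests on grading the erythema score on Table 4 and on the absence of any order of precedence between synopsis and body. It does not depend on an assumed event rate. The figure above 1 may be a slip for a score of 1; if so, it is a slip in the instruction that sets the delivered dose. The point does not show that a patient would be overtreated, only that 6.2.3.1 as written permits it.

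**What to change.** In the 6.2.3.1 visit bullet, replace the score above 1 with an erythema score of 1 (Grade 1) and keep the 25 J/cm² cap, whichever comes first.

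In the 6.2.3.1 narrative, replace the permissive sentence with the synopsis rule: reduce the light dose at Grade 2; at Grade ≥3 suspend for one week, with any restart 1 J/cm² below the last well-tolerated dose.

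If keeping the dose at Grade 2 is intended, amend the synopsis to say so, but make the Grade ≥3 stop compulsory in the body. Repeating the cap in the synopsis and in 6.1 would be optional tidying.

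These are wording changes with no new assessment, visit or data field. The price is slightly less investigator discretion at Grade 2 and above.

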6.2.3.2.1 Light Treatment Day

The patient will return to the clinic 21 (± 3) hours after study drug is applied and the following assessments will be conducted prior to light treatment:

- Each index lesion will have an mCAILS score assessed and recorded
- The mSWAT score will be assessed and recorded
- The PGA score will be assessed and recorded
- The SAEQ score will be collected and recorded
- The SCORD score will be collected and recorded

Once the assessments are completed, the standard light treatment procedures will be conducted, as follows:

- Interval medical history obtained
- Any AEs documented
- Adequate application of the drug will be verified by a pink staining on visual inspection of lesions
- Delivery of light session, the time of treatment calculated by the target dose
- A dermatologic assessment of treated lesions will be performed immediately before and 10 to 30 minutes following completion of the light session. This includes assessment of treated lesions and surrounding areas for:
 - Erythema

- Pain
- Pruritus
- Edema
- Hyperpigmentation
- Hypopigmentation
- Rash
- Vesication

6.2.3.3 Week 12 Session 24

6.2.3.3.1 Light Treatment Day

The patient will return to the clinic 21 (± 3) hours after study drug is applied and the following assessments and procedures will be conducted **prior to** light treatment:

- Each index lesion will have an mCAILS score assessed and recorded
- The mSWAT score will be assessed and recorded
- The PGA score will be assessed and recorded
- The SAEQ score will be collected and recorded
- The SCORD score will be collected and recorded
- Physical Exam
- Vital Signs obtained
- Blood for the hematology panel obtained
- Blood for the clinical chemistry panel obtained

Once the assessments are completed, the standard light treatment procedures will be conducted, as follows:

- Interval medical history obtained
- Any AEs documented

- Adequate application of the drug will be verified by a pink staining on visual inspection of lesions
- Delivery of light session, the time of treatment calculated by the target dose
- A dermatologic assessment of treated lesions will be performed immediately before and 10 to 30 minutes following completion of the light session. This includes assessment of treated lesions and surrounding areas for:
 - Erythema
 - Pain
 - Pruritus
 - Edema
 - Hyperpigmentation
 - Hypopigmentation
 - Rash
 - Vesication

6.2.3.4 Follow-Up Visits (Week 13, 14, and 16)

Patients will return to the clinic during Weeks 13, 14, and 16 (End of Study) for follow-up assessment. At each follow-up visit, the following will be conducted:

- Interval medical history obtained
- Any AEs documented
- Each index lesion will have an mCAILS score assessed and recorded
- The mSWAT score will be assessed and recorded
- The PGA score will be assessed and recorded
- The SAEQ score will be collected and recorded
- The SCORD score will be collected and recorded
- Vital signs obtained

In addition to the assessments above, the following will be done at the Week 16 Follow-Up/End of Study visit:

- Physical Exam
- Vital Signs obtained
- Blood for the hematology panel obtained
- Blood for the clinical chemistry panel obtained

6.2.4 Valchlor Patients

Patients who are randomized into the Valchlor treatment arm will be given a tube of gel at the Baseline visit. They will be instructed on proper drug application according to the instructions on the package insert.

6.2.4.1 Week 3, Week 6, and Week 9

Patients will be instructed to come to the clinic during Weeks 3, 6, and 9.

At the clinic, the following assessments will take place before Valchlor is applied:

- Interval medical history obtained
- Any AEs documented
- Each index lesion will have an mCAILS score assessed and recorded
- The mSWAT score will be assessed and recorded
- The PGA score will be assessed and recorded
- The SAEQ score will be collected and recorded
- The SCORD score will be collected and recorded
- Vital signs obtained

Once these assessments have been completed, the patient will apply study drug at the clinic.

6.2.4.2 Week 12

Patients will come in to the clinic at Week 12, and the following assessments and procedures will be completed before Valchlor is applied:

- Interval medical history obtained
- Any AEs documented
- Each index lesion will have an mCAILS score assessed and recorded
- The mSWAT score will be assessed and recorded
- The PGA score will be assessed and recorded
- The SAEQ score will be collected and recorded
- The SCORD score will be collected and recorded
- Physical Exam
- Vital Signs obtained
- Blood for the hematology panel obtained
- Blood for the clinical chemistry panel obtained

Once these assessments and procedures have been completed, the patient will apply study drug at the clinic.

6.2.4.3 *Follow-Up Visits (Week 13, 14, and 16)*

Patients will return to the clinic during Weeks 13, 14, and 16 (End of Study) for follow-up assessment. At each follow-up visit, the following will be conducted:

- Interval medical history obtained
- Any AEs documented
- Each index lesion will have an mCAILS score assessed and recorded
- The mSWAT score will be assessed and recorded
- The PGA score will be assessed and recorded
- The SAEQ score will be collected and recorded
- The SCORD score will be collected and recorded
- Vital signs obtained

In addition to the assessments above, the following will be done at the Week 16 Follow-Up/End of Study visit:

- Physical Exam
- Vital Signs obtained
- Blood for the hematology panel obtained
- Blood for the clinical chemistry panel obtained

